3 INTRODUCTION

3.1 Background & Rationale

Diabetes represents a major national and global health problem. Eighty-eight million adults in the US and 352 million individuals worldwide have prediabetes, with 1.5 million Americans transitioning to diabetes annually.¹ Preventing or delaying this conversion from prediabetes to diabetes would be a major medical advance that could improve the health of many individuals and reduce health care costs.

Metformin is a frequently used but often suboptimal treatment for preventing the progression of prediabetes to diabetes. One study found that one third of patients initiating metformin discontinued use within one year, and less than half of all patients are adherent to metformin.² Some patients experience intolerable symptoms, and long-term use of metformin is associated with anemia and declining cognitive function.^{3 4 5 6 7}

Intensive lifestyle interventions hold promise as cost-effective treatment for prediabetes.⁸ Conventionally, this approach involves weight loss of at least 7% and at least 150 minutes a week of moderate to vigorous physical activity, with a recommended year-long intervention.⁹ Weight loss and moderate to vigorous physical activity can both prevent, delay, and treat the progression of prediabetes to type 2 diabetes (T2D).^{10 11} However, weight-loss lifestyle interventions are inappropriate for lean individuals, unwanted by others, and unsuccessful or unsustainable for other patients.¹²¹³

3.2 Glycemic Excursion Minimization

We found that a lifestyle management of T2D that reduces glycemic excursions (area under the curve - AUC) is an effective alternative treatment of T2D.^{14 15 16 17 18 19} Our NIH funded research demonstrates that Glycemic Excursion Minimization (GEM) guide is more effective than weight loss alone in lowering A1c, reducing BMI, decreasing cardiovascular risk, and improving psychological functioning. Moreover, the efficacy of GEM appears broadly applicable since it is unrelated to baseline demographic, psychological, or disease severity variables. Furthermore, GEM sustains these benefits over a 13-month follow-up and without needing an intervening maintenance program. Additionally, our recent Abbott study found that GEM combined with CGM significantly improves A1c, glucose area under the curve, weight, and psychological functioning of adults recently diagnosed with T2D, and achieves this benefit with less diabetes medication.¹⁹ These observations provocatively raise the following question: Is GEM plus CGM similarly an effective means of preventing the progression of prediabetes to T2D?

GEM is an appealing therapeutic strategy. GEM involves: 1) educating patients regarding how their choices impact both their current and future blood glucose (BG) fluctuations, 2) empowering individuals to make choices in the timings, amounts, and types of foods that diminish BG elevations, and 3) choosing types, amounts, and timings of physical activities that hasten the recovery of BG excursions. This approach presumes accurate and timely feedback of BG status to: a) educate patients regarding the impact of their choices, b) activate patients to take appropriate action when BG excursions are beyond their desired goals, c) motivate patients to repeat choices that either diminish extreme BG excursions or correct undesired BG excursion status, and d) investigate new food and activity choices to evaluate how they impact their BG excursion status.

More investigation needs to be done to establish the importance of CGM in treating prediabetes. Yost et al's investigation of CGM and low carbohydrate diets of adults with prediabetes²⁰ suggested that CGM plus a low carbohydrate diet was acceptable to their sample, led to lower A1c, and reduced sense of vulnerability to developing diabetes. However, it had multiple limitations that will be addressed by our proposed study: briefly, the aforementioned article 1) only had 20 days of CGM, 2) did not have a routine care group to distinguish the effects of diagnosis and enrollment in a study on A1c, AUC, weight reduction, etc., 3) did not measure A1c before and after their intervention, 4) required three face-to-face and two telephone patient contacts, 5) employed a primary outcome that was satisfaction with CGM and low carbohydrate diets, and 6) had a subject sample that was narrow, requiring a BMI of >30. In addition, our study will include the combination of the GEM manual and CGM to actively teach subjects how to interpret, predict, and effect the CGM results which is hypothesized to be a more active and powerful behavioral modification.

Our proposed investigation addresses many of the aforementioned limitations by focusing on reducing AUC rather than weight or CGM time above 180. Thus, GEM targets reducing post prandial, as well as periodic post snack and drink, glucose excursions. Our approach would employ two groups (with no weight restriction) to identify the effects of participation in a study. Our primary outcome variable of reduction in AUC (reduced % CGM readings above 120) is more appropriate to our patient sample. GEM requires no face-to-face visits. In contrast to the above studies that use

CGM to educate either the patient or artificial intelligence, GEM uses CGM feedback to educate, motivate, activate, and investigate. Additionally, our proposed study will also allow us to explore two preliminary issues: [name] has developed the Treatment Optimization Scale that is intended to predict which patients are more likely to do better on medication or lifestyle intervention. We anticipate that individuals with a strong preference to actively engage in a lifestyle intervention will do better on CGM and in the GEM group. Additionally, we will begin to explore proteomics in the study population, as described below.

3.3 Proteomics

Measuring plasma proteome changes could further enhance the proposed observations and provide new opportunities for advancing the management of patients with prediabetes.²¹ We also propose to sequentially (before, during crossover, and after treatment) measure and analyze the plasma proteome using SomaScan analyses of ~7,500 proteins on a small sample of heparinized plasma (~2cc). This preliminary analysis will begin to characterize the effects of our treatment approach on inflammatory, oxidative stress, and other plasma proteins and protein pathways that change during the evolution of pre-diabetes to diabetes. This data could suggest further testing of specific biomarkers that could be used in the future to guide or assess treatment strategies to perhaps identify responders and non-responders—a more personalized approach and one that ultimately might provide additional impetus for individuals to monitor their glucose levels using CGM and to adhere to treatments that improve their CGM assessments. A recent article (2021) in E BioMedicine emphasizes the importance of characterizing this patient population using comprehensive proteomic approaches.²² Briefly, the authors discovered that: (a) a broad range of blood-borne proteins are altered at the very early stage of screening-detected T2D patients, and (b) that newly identified protein patterns reflect key metabolic syndrome features such as insulin resistance, fatty liver disease, hyperglycemia, and adiposity as well as other protein pathways associated with diabetes. In addition, and importantly, proteomic changes observed at baseline were significantly attenuated during metabolic improvement associated with metformin treatment. They lauded their proteomic approach for its potential to predict diabetic status with high accuracy from the protein signature and as a way to deliver improved and more individualized health care.

3.4 Risk / Benefit Assessment

We assess this trial as posing **no greater than minimal risk**.

4 OBJECTIVES

We will investigate whether providing CGM within a structured, self-directed and personalized program (GEM) will allow participants with prediabetes to improve their metabolic status by illustrating the effects of their routine food and

physical activity choices on their blood glucose levels and variability, more than Routine Care (RC). We will enhance these investigations by adding comprehensive plasma proteomics to the analyses.

4.1 Primary Objective

The primary outcome variable will be participants' pre-post reduction in percentage of CGM readings >120, from blinded pre-post LibrePro. This is most relevant since the goal of GEM is to reduce glucose excursions and since 13% of non-diabetic adults' CGM readings exceed 120.²³

Our hypothesis is that participants assigned to the intervention group will achieve a greater pre-post reduction in percentage of CGM readings >120 than will the control group.

4.2 Secondary Objectives

- To assess the reduction in A1c and Libre Pro glucose variability²⁴
- To assess reduction in BMI
- To assess reduction in cardiovascular risk defined by UKPDS²⁵ and the ASCVD risk²⁶
- To assess improvement in psychological function as defined by improvement in empowerment, measured through a modified Diabetes Empowerment Scale²⁷, fewer depressive symptoms,²⁸ and a modified Diabetes Knowledge Scale
- To measure dietary habits using Carbohydrate Routine Consumption Scale²⁹
- To obtain data exploring psychological measures determining "readiness to change" using the MATCH and Treatment Optimization Scale.
- To obtain data exploring physiological proteomics measures. This will be addressed by analyzing individual proteins and protein pathways measured through the use of a multiplex proteomics platform that has been used in other clinical trials to characterize differential mechanistic effects that may identify eventual responders from non-responders.
- To obtain program feedback using the Program Importance Questionnaire

[figure not shown]
5 STUDY DESIGN

5.1 Study Overview

This is a single center, 2 between (groups) x 2 within (pre-post) partial cross-over randomized clinical trial. A total of up to 70 subjects will be enrolled to allow for screen failures and up to 20% anticipated attrition, with the goal of ending the study with 20 subjects completing the GEM intervention, including those who crossover from the routine care arm for a total of 30 subjects completed an arm and/or both arms. Subjects who meet all inclusion criteria and none of the exclusion criteria will be entered into the study after informed consent.

Participants will be randomized to RC or GEM (2:1) where RC participants will have the opportunity to receive GEM four months after consenting and completion of the RC pre-post assessments. It was anticipated that 50% of the RC participants would want to and be able to cross over to GEM upon completion of RC.

However, 50% of our RC participants at post assessment did not qualify to cross over due to A1c being outside the 6.0-6.4 inclusion criteria range. This left less than 50% available to cross over to GEM, far fewer than anticipated. Given this reduced sample we will go from a 2:1 to a 1:1 randomization to RC. This allows allocating more participants directly assigned to GEM, thus relying less on RC crossovers. Given that this is a feasibility study and there were fewer participants that could cross over from RC to GEM due to post Routine Care A1c, the decision was made to change the randomization to 1:1. The investigator team felt this change was necessary in order to ensure that adequate data was collected from this feasibility study to power a larger study.

There will be 2 groups:

- Group 1. Routine Care (RC) participants will follow recommendations from their primary care providers. These recommendations will be tracked for later analyses.
- Group 2. GEM participants will be given Libre 2 supplies for 4.5 months, an activity monitor and the 4-chapter paper GEM guide which provides: 1) decisive didactic information about the effects of net carbohydrate consumption and routine physical activity on blood glucose fluctuations; 2) instructions to systematically use CGM feedback to educate them about how carbohydrates and physical activity impact their BG excursions, motivate them to repeat choices that lead to lower AUC, activate them to take steps to lower their BG elevations when detected by the high glucose alarm, and investigate the BG impact of new food and activity choices

concerning their effect on their BG; 3) employ structured self-monitoring (diary) to organize and identify personal patterns in their food and physical choices that impact their AUC; 4) GEM Supplement that provides additional information to the manual, e.g. frequently asked questions and answers, nutrient content of low glycemic load foods, case reports, youtube exercise videos; and 5) automated personalized daily text messages to “choose wisely” food and activity choices, and perform daily diary entries. The GEM manual for this prediabetes sample will follow the same format as that used with our diabetes sample: 1) become aware of metabolic costs of routine choices, 2) minimize BG elevations with personally relevant food choices, 3) hasten BG recovery with increased routine physical activity, and 4) plan for continuation of such lifestyle changes. The major adaptation in the GEM Guide for this prediabetes population focused on reducing risk of progression to diabetes and having to initiate diabetes medications. The GEM Guide was adapted based on clinical experience, the qualitative analyses of Yost et al,²⁰ and the literature on secondary prevention.³⁰

Given that this is a pilot study, we did not perform a formal power analysis at this time because there are no data suggesting anticipated change in AUC for adults with prediabetes. However, 20 participants completing the GEM path through the study will provide data to estimate this effect size and therefore to enable power analysis for an anticipated follow-up NIH application. Additionally, N=15 was sufficient to find a pre-post effect in a previous study evaluating a different intervention in a prediabetes population.²⁰

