11.3 Analysis of Primary Endpoint

The proposed study is a 2 between (groups) x 2 within (pre-post) partial cross-over randomized clinical trial. The primary endpoint of % glucose <120 will be compared between groups for study period 1 using t-tests; within the cross-over group for study period 2 using paired t-tests..

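### Section 5.1 takes the follow-up trial's effect size from 20 people who all receive GEM, some of them re-selected crossovers, and not from the randomised period-1 GEM minus RC difference

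*Combined protocol and SAP*

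**What the plan says.** Section 5.1 gives no power calculation because "there are no data suggesting anticipated change in AUC for adults with prediabetes". It then says that "20 participants completing the GEM path through the study will provide data to estimate this effect size" and so "to enable power analysis for an anticipated follow-up NIH application". In support of the size it adds that "N=15 was sufficient to find a pre-post effect in a previous study evaluating a different intervention in a prediabetes population". Section 3.2 treats AUC and the share of CGM readings above 120 as the same outcome, so the effect size in question is a change in the primary endpoint.

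The same section defines who the 20 are: "20 subjects completing the GEM intervention, including those who crossover from the routine care arm for a total of 30 subjects". Section 6.2 restates the count as 20-24 and ties it to half of RC crossing over. Sections 5.1 and 9.5.1 and Appendix 1 make crossover conditional on still being eligible on A1c. Section 5.1 reports that "50% of our RC participants at post assessment did not qualify to cross over due to A1c being outside the 6.0-6.4 inclusion criteria range", and for that reason moves allocation from 2:1 to 1:1.

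A randomised contrast is also planned. Section 4.1 states a between-group hypothesis, section 11 names a two-group ANCOVA of change with baseline covariates, and section 11.3 compares groups in period 1. For period 2, section 11.3 analyses change "within the cross-over group for study period 2 using paired t-tests".

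**The concern.** The estimate named for planning is not the one the trial is randomised to provide. Everyone who completes the GEM path has had GEM, so those people's data can show only how much they changed, not how much more they changed than they would have under RC. Section 3.2 faults an earlier pilot because it "did not have a routine care group to distinguish the effects of diagnosis and enrollment in a study", and gives identifying participation effects as the reason for having two groups. The sample-size rationale then sets that comparison aside, and the precedent it cites is also a pre-post result.

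The crossovers add a second difficulty. They qualified on A1c at entry, possibly after the re-screening allowed in section 9.2, and must qualify again at the end of RC. They are therefore an A1c-selected part of the RC arm, observed in period 2 with no one alongside them.

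What is at stake is the size of the next trial. A randomised follow-up tests a between-group difference. If it is sized on a pre-post change, its sample size is wrong by whatever RC participants would have changed anyway.

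**Working it through.** **1. Inputs.** From the documents: 36 enrolled and at least 30 completing (Protocol Summary); RC:GEM 2:1, later 1:1 (section 5.1); planned crossover 50% of RC (sections 5.1 and 6.2). The documents give no SD, effect size, alpha or power. Those used below are assumptions.

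**2. Reproducing the 20.** GEM path = randomised GEM + crossover rate x RC.
- 30 completers at 2:1: 10 + 0.5 x 20 = 20, the figure in section 5.1.
- 36 enrolled at 2:1: 12 + 0.5 x 24 = 24, the upper figure in section 6.2.
- 30 completers at 1:1: 15 + 0.5 x 15 = 22.5, or 15 + 0.25 x 15 = 18.75 if only a quarter cross over (assumed).

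Randomised GEM alone gives 10 completers (2:1) or 15 (1:1). As planned at 2:1, half of the 20 are crossovers. The number randomised before the ratio changed is not given, so the actual mix lies between these cases.

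**3. What each estimate measures.** Let B be the mean change the same people would show without GEM (drift, participation, regression to the mean).
- Mean change in GEM-path completers = GEM effect + B.
- Period-1 GEM minus RC = (GEM effect + B) - B = GEM effect.

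**4. Effect on the follow-up's size.** Write D for the pre-post change under GEM and B = rD. The between-group effect is then (1-r)D. Required N varies as 1/effect^2, so for the same SD the needed N is 1/(1-r)^2 times the N planned on D.
- r = 0.25: 1/0.5625 = 1.78.
- r = 0.5: 1/0.25 = 4.
- r = -0.25 (RC worsens): 1/1.5625 = 0.64, so the planned N is larger than needed.

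Illustration with an assumed standardised pre-post change of 0.8, two-sided 5%, 80% power and n per arm = 2(1.96 + 0.8416)^2/d^2 = 15.70/d^2. Planning on d = 0.8 gives 25 per arm. Power at that size is Φ(d√(25/2) - 1.96).

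| r (assumed) | true d | n per arm needed | power at 25 per arm |
|---|---|---|---|
| 0 | 0.8 | 25 | 81% |
| 0.25 | 0.6 | 44 | 56% |
| 0.5 | 0.4 | 99 | 29% |

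At r = -0.25 the true d is 1.0 and 16 per arm would be enough. The loss of power for positive r is about the same if the assumed pre-post change is 0.5 or 1.0.

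**5. Precision of the two estimates**, as 95% half-widths in units of the SD of change:
- 20 GEM-path completers, one sample: t(19)/√20 = 0.47.
- 15 GEM vs 15 RC: t(28) x √(1/15 + 1/15) = 0.75.
- 10 GEM vs 20 RC: t(28) x √(1/10 + 1/20) = 0.79.

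The pre-post interval is narrower, but it is an interval for GEM effect + B.

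**The case against.** The strongest reply is that the controlled estimate is already in the plan. The hypothesis is between-group, section 11 has the ANCOVA, section 11.3 compares the arms in period 1 and keeps the two periods apart, and the move to 1:1 was made to rely less on crossovers. On this view section 5.1 is loosely worded and little else is wrong. Much of this stands: the primary comparison is untouched, the harm falls on a later application, and one sentence would repair it. But section 5.1 does name a source for the effect size, and that source contains no RC data.

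Some stronger readings are tempting and the documents do not support them.
- *That the plan will pool randomised GEM and crossovers in one analysis.* Section 11 specifies no such analysis. Section 5.1 counts them together and names that count as the source of the effect size, and it goes no further.
- *That the follow-up would be underpowered.* This needs RC to improve. The A1c band has two ends, and section 5.1 does not say whether the half outside it were below 6.0 or above 6.4.
- *That this half measures regression to the mean in the primary endpoint.* It concerns A1c. Baseline CGM is placed at or after the qualifying A1c (section 9.2), so error in that A1c reading does not enter the CGM baseline. Only real fluctuation in glucose could, and the documents give no figure for it.
- *That powering the next study is the pilot's only purpose.* It is one stated use. The primary objective is metabolic control.
- *That the period-2 paired t-test must go.* Section 11.3 does not present it as proof of efficacy or tie it to planning. Labelling it is enough.

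**Conclusion.** The point holds as a should-fix. As written, section 5.1 assigns the follow-up's effect size to an uncontrolled within-person change in a group that reaches 20 only with A1c-selected crossovers. That is the wrong quantity for a randomised follow-up, and it departs from the protocol's own hypothesis and its stated reason for having an RC arm.

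That conclusion rests on the text and on the count 10 + 0.5 x 20 = 20. The size of the error does not: the factors 1.8 and 4 depend on assumed values of r, and the per-arm numbers also on an assumed standardised change of 0.8. Neither the direction nor the amount of bias can be derived from the documents.

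**What to change.** In section 5.1, state that the planning effect size is the period-1 randomised GEM minus RC difference in change, adjusted for baseline by the section 11 ANCOVA, reported with its residual SD and with 95% confidence intervals for both. Section 11.3 names t-tests for the same comparison, so the text should say that the ANCOVA estimate is the one carried forward.

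In section 11.3, label the crossovers' period-2 pre-post change as descriptive data on an A1c-selected subset. Report it separately with a confidence interval, and do not combine it with randomised GEM for planning.

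Only wording changes; no visit, measurement or sample size is affected. The price is an openly wider interval: a half-width of about 0.75 SD at 15/15 or 0.79 SD at 10 GEM/20 RC, with the actual split somewhere between, against 0.47 SD for the uncontrolled 20. A follow-up planned on it will have to allow for that uncertainty.

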5.2 Criteria for evaluation

5.2.1 Data Collected

- Demographics (e.g., sex, age, race, smoking)
- Vital signs (e.g., height, weight, blood pressure)
- Lab tests (e.g., A1c, lipids)
- FitBit data
- Psychosocial scales (e.g., Carbohydrate Routine Consumption Scale, MATCH scale, PHQ-8 depression scale)
- Comprehensive proteomics

5.2.2 Primary Endpoint

- pre-post reduction in percentage of CGM readings >120, from blinded pre-post LibrePro.

5.2.3 Secondary Endpoints

- reduction in A1c and Libre Pro BG variability
- reduction in BMI
- reduced cardiovascular risk defined by UKPDS and ASCVD risk calculator.
- improvement of psychological function as defined by a greater sense of modified diabetes empowerment, fewer depressive symptoms, and improved modified diabetes knowledge.

- To obtain data exploring psychological measures determining “readiness to change” using the MATCH scale, and Treatment Optimization Scale
- To obtain data exploring physiological proteomics measures. This will be addressed by analyzing individual proteins and protein pathways measured through the use of a multiplex proteomics platform that has been used in other clinical trials to characterize differential mechanistic effects that may identify eventual responders from non-responders.

